## 12.4 Appendix D: Additional Site-Led HCS Research Activities

HCS RSs may seek approval from the Steering Committee and NIDA for site-led research activities. Steering Committee and NIDA approved protocols, once approved by the IRB, may be implemented by a single site, two to three sites, or as many as all sites, based on local preference.

### 12.4.1 Group Model Building Workshop

The New York RS will conduct a group model building (GMB) workshop (see *Group Model Building Workshop Facilitation Manual*) that aims to advance the site's understanding of how community coalitions conceptualize the organizational dynamics that affect OUD and how the CTH is implemented in their communities. GMB is a qualitative method used to develop a causal loop diagram or systems dynamic model, which are constructions of explicit models, or representations, of a system's behavior, considering multiple actors, factors, levels, and the interconnections and feedbacks among them. Systems models can help test the potential effect of interventions and identify the points of maximum leverage in the system.

Community coalition members and other local stakeholders will be asked to participate in the GMB workshop. During the GMB workshop, participants will present their understanding of the driving factors and etiology of OUD in the context of their community's organizational dynamics. Based on this information, a causal loop diagram or systems dynamic model will be developed.

Participants will not be forced to disclose or discuss any information they do not feel comfortable sharing, and the confidentiality of study participants' information will be protected throughout the general study protocols. The GMB process focuses on documenting participants' perceptions and ideas about the opioid crisis and potential solutions at the community level. No individual health information will be collected. In addition, participant names or identifying information will not be used in research reports or presentations.

### 12.4.2 GetNaloxoneNow

Overdose education is part of the ORCCA EBP selection for communities. All four RSs will provide HCS communities with the option of using [www.GetNaloxoneNow.org](http://www.GetNaloxoneNow.org).

GetNaloxoneNow is an online resource to train people to respond effectively to an opioid overdose emergency. The content of the GetNaloxoneNow module draws on years of scholarship and contributions of many experts in overdose prevention including public health researchers, harm-reduction specialists, physicians, nurses, police officers, firefighters, emergency medical technicians, case managers, outreach workers, graphic designers, professional actors, and educators. Funding to develop the training module was provided by NIH/NIDA, Grant #1R43D033746-01 and Grant #1R43DA029358-01A1 (PI: [name]). This online overdose education is an evidence-based practice that includes a bystander (i.e., general public) module and a first responder module. The GetNaloxoneNow bystander training module is about 20 minutes, and the first responder training module is approximately 45 minutes.

The four HCS RSs will obtain monthly data analytics on the number of individuals who start and complete the bystander and the first responder training module by county and state through Co-Investigator [name]. As part of the registration process for this existing training, demographics are collected, including race/ethnicity, preferred language, gender, age range,

self-report of overdose, or witnessed overdose, as well as other questions related to how they heard about the training. There are also post-training questions to assess the ability to intervene in the case of overdose.

HCS sites will receive only de-identified aggregate data describing participants; therefore, informed consent is not required.

De-identified data will include the following:

- Demographics including race/ethnicity, preferred language, gender, age range, self-report of overdose, or witnessed overdose
- County, state of residence, and ZIP Code
- Questions related to how they heard about the training
- Post-training module questions to assess ability to intervene in case of overdose

Data transfers will occur monthly during the period from January 1, 2020, through March 31, 2023. Data will be stored in local, approved informatics environments for at least 3 years.

#### **12.4.3 Brandeis University Collaboration to Conduct Interviews with Health Care Payers**

Brandeis University is collaborating with the Massachusetts RS, and Brandeis University staff will conduct semi-structured interviews with health care payers in Massachusetts, as part of the HEALing Communities Study (HCS). This activity is site specific to Massachusetts and is supervised by the HCS's Implementation Science Core at Boston Medical Center.

The interviews are intended to gather information about the extent to which payers currently fund or otherwise encourage activities that communities may adopt as part of the HCS intervention, such as medications for opioid use disorder (MOUD), distribution of naloxone, or initiatives in schools, pharmacies and law enforcement settings. There is also interest in the extent to which payers would be willing to fund those activities in the future, and how they make decisions about which activities to fund or otherwise support. The resulting information may be helpful to determine the long-term sustainability of the system interventions that are being tested in the HCS communities.

The Brandeis University team will seek to interview officials at MassHealth (the state Medicaid program) and at commercial insurers that serve Massachusetts customers. In 2018, the Massachusetts Division of Insurance identified 13 commercial insurers serving Massachusetts. The team will identify the official at each institution most likely to have knowledge about policies toward opioid use, MOUD, and other topics of interest. For insurers that contract out the management of substance use disorder treatment to an external vendor, the team will also seek to interview that vendor (e.g., for MassHealth: Beacon Health Options, and the Medicaid managed care plans). A total of up to 20 interviews will be conducted. In some cases, these persons are already known to the team from prior research with local health plans. In other cases, the team will use other information to identify the best respondent, using contacts from professional networks and information from company websites and elsewhere.

The team will contact potential participants by email, to explain the HCS study and ask if they are willing to participate in an interview. If an official agrees to an interview, the team will schedule the interview. The team will ask the respondent to complete a survey (via REDCap) that includes a few pre-interview questions on factual issues, such as whether their plan covers certain specific opioid use disorder-related services, whether it provides incentive payments to providers, etc.

The interview will last up to one hour and will be an open-ended discussion. Each respondent will be asked a series of open-ended questions about their institutional policies and activities in relation to MOUD or naloxone, including both use of reimbursement/incentives and other forms of encouragement to providers. The interview will not ask respondents about their own beliefs or their own experience with health care. The interviews will be conducted annually for the duration of the study. After baseline, the team will ask about changes since baseline, and what effect, if any, the HCS initiative played in any resulting policy changes.

Neither the pre-interview survey nor the interview will collect PHI/PII from the respondent.

The interview will be audio recorded. The recording is for the use of the Brandeis University research team in transcribing the interviews and will not be shared with anyone outside of the research team. The recording may include the respondent's name, but it will be removed from the transcribed interview form and a study ID number substituted in its place. The audio files and transcription will be saved on a secure server at Brandeis University. Audio files will be destroyed within 6 months following transcription; transcription files will be kept for 3 years following project completion and then destroyed.

Brandeis University will analyze the interview transcripts using qualitative data techniques. The team will summarize the results in annual reports to the Boston Medical Center's HCS leadership team and may use the results in future publications.

#### **12.4.4 Academic Detailing and CECentral Online Modules**

To facilitate and operationalize ORCCA EBP Requirement 3: Safer Opioid Prescribing and Dispensing at the service provider level, and address barriers for rural healthcare providers, the Kentucky RS has developed Academic Detailing and On-Demand Online Continuing Education modules through CECentral. Components include Academic Detailing (in-person training) as well as online modules for Pain Management for Pharmacy, MOUD for Pharmacy, Safer Opioids and Overdose Risk Reduction, and Naloxone Training. Audience will be dentists, nurse practitioners (primary care), pharmacist, pharmacy technicians, and physicians (primary care). Educational content meet accreditation standards, compliance documentation, and outcomes assessment for AMA PRA Category 1 Credits™, ACPE contact hours/CEUs, Dentistry credit, and participation certificate, as well as House Bill 1 requirements for dentists, nurse practitioners, and physicians. Both Academic Detailing and On-demand Online CE modules will be provided free of charge.

As part of the registration process, CECentral requires pre-activity evaluation questions and post-activity evaluation questions. To assess the impact of Academic Detailing and On-Demand Online Education on safer opioid prescribing and dispensing, the Kentucky RS will receive de-identified data describing registrants. Because data received will be de-identified, informed consent is not required.

De-identified data may include the following:

- Demographics (profession)
- Practice Information (county of primary practice)
- Pre-activity questions to assess knowledge, attitudes, and current practice standards/processes
- Post-activity questions to evaluate knowledge, change in attitudes, and impact on practice standards/processes
- Post-activity questions to assess the delivery and content of educational modules and speakers

Data transfers will occur quarterly (March 31, June 30, September 30, December 31) beginning September 30, 2020, through March 31, 2023. Data will be stored in secure, local, approved informatics environments for at least 3 years.

#### **12.4.5 MOUD Organization Interview Guide**

University of Kentucky research staff will conduct small group semi-structured interviews with staff working in organizations that provide medication for opioid use disorder (MOUD) in Kentucky, as part of the HEALing Communities Study (HCS). This activity is site-specific to Kentucky and is supervised by the HCS's Implementation Science and Treatment teams at the University of Kentucky.

The interviews are intended to gather information about barriers to access and retention in MOUD as well as the impacts of COVID on the delivery of MOUD within the Kentucky HCS communities. The resulting information may be helpful in explaining the potential impacts of efforts to implement aspects of Menu 2 in the Opioid-overdose Reduction Continuum of Care Approach (ORCCA).

The University of Kentucky team will seek to conduct small group semi-structured interviews with staff working in organizations providing MOUD, which include, but are not limited to, opioid treatment programs (OTPs), non-OTP specialty substance use disorder programs, and office-based medical practices. It is anticipated that approximately 2-3 staff from a given organization will participate in the interview, but some interviews may be conducted with a single individual. To identify potential interviewees, the team will draw upon information provided by the community's HCS coalition, individuals in MOUD organizations that have already implemented fast-track overdose education and naloxone distribution, the team's professional networks, the Drug Enforcement Agency's list of waivered providers, and MOUD organizations' websites. It is anticipated that efforts will be made to conduct interviews with all agencies that have been identified for Menu 2 implementation within the eight Wave 1 communities; similar interviews will be conducted once HCS moves into Wave 2. Up to 250 individuals will be interviewed.

The team will contact potential participants by email or telephone to explain the HCS study and ask if they are willing to participate in a small group interview. Each small group interview will only include individuals from a single organization. If individual(s) from the organization agree to an interview, the team will schedule the interview. During the interview, participants will be asked open-ended questions about the organization's MOUD census, resources needed to increase the patient census, barriers to MOUD access and retention, differences in barriers

between types of MOUD (if the organization offers more than one type of MOUD), the impact of the COVID-19 pandemic on MOUD delivery and use of telehealth for MOUD. Because of the semi-structured nature of the interview, interviewers may probe for clarity or greater detail. The interview guide will not ask individuals about their personal beliefs or their personal experience with health care. A brief demographic REDCap survey, using the IRB approved *HCS Demographic Form* will be used to collect information on race, ethnicity, gender, age, and education after the interview.

Neither the interview nor post-interview demographic survey will collect PHI/PII from the respondent.

The interview will be audio-recorded and professionally transcribed. Identifying information will not be shared with anyone outside of the research team. The recording may include the names of individuals or organizations but identifying information will be removed from the interview transcript and a study ID number substituted in its place. The audio files and transcription will be saved on a secure server at the University of Kentucky and destroyed 3 years following project completion. Demographic data will be stored within REDCap on secure servers.

The University of Kentucky team will analyze the interview transcripts using qualitative data techniques. Findings may be reported in peer-reviewed manuscripts, but confidentiality will be maintained by not identifying any individuals or organizations in publications.

#### **12.4.6 Pharmacy Study Interview Guide & Survey**

The New York research site will conduct a survey with selected pharmacies and Pharmacists, as well as interviews with Pharmacists and community members as part of the HEALing Communities Study (HCS). This activity is site-specific to New York and is supervised by Columbia University School of Social Work Associate Research Scientist [name], Ed.D.

The survey and interviews are intended to assess racial and ethnic disparities in Medication for Opioid Use Disorder (MOUD) and Naloxone availability at pharmacies in HCS communities, and to examine the perspectives of People with Opioid Use Disorder (PWOUD) with respect to barriers to accessing MOUD and Naloxone services in pharmacies. There is also interest in using these findings to inform the use of pharmacies to promote MOUD and Naloxone as part of the HCS intervention and to increase engagement, participation, and leadership of more ethnic minorities in the community coalitions and overall HCS study.

Members of the New York research team will seek to survey (via two different surveys [one for pharmacy staff or pharmacists and one specifically for licensed pharmacists]) a sample of Pharmacists, pharmacy technicians and/or other pharmacy staff who work for pharmacies in New York's HCS communities. The NYS Pharmacy Association will provide recruitment assistance to the research team that will also conduct an online search for pharmacy contact information. The surveys will be programmed in REDCap and will include questions about access to Narcan/Naloxone, Buprenorphine, Naltrexone, Methadone and COVID-19 testing in pharmacies in the HCS communities. The surveys will take between 20 and 30 minutes to complete. Respondents can choose to participate via a REDCap link sent to their email or to complete the survey by phone with a NY research site staff member.

Members of the New York research team will also conduct semi-structured one-on-one interviews with a sample of community members (including African Americans and Hispanics) with a goal of interviewing 20 People with Opioid Use Disorder (PWOUD) and 20 pharmacists in HCS communities.

Through the assistance of its community coalitions, the New York team will recruit individuals and receive referrals from three types of programs serving PWOUD at sites in NY's HCS counties with diverse communities: (a) one methadone maintenance treatment program (MMTP); (b) one primary care clinic; and (c) one syringe exchange program (SEP). Recruitment will ensure that the sample includes minority representation across non-Hispanic Blacks and Hispanics.

New York research staff will explain the study to potential PWOUD participants and verify their age and drug use experience. To be eligible, PWOUD study participants must be: 18 years of age or older, have used heroin, cocaine, and/or methamphetamine within the past 12 months, and/or received, or currently receive services from an opioid treatment, HIV primary care, or a syringe exchange program.

The research team will contact potential participants by email to explain the HCS study and ask if they are willing to participate in an interview. If the potential participant agrees to participate, the team will schedule the interview. The interview will last approximately 45 minutes and will be an open-ended discussion. Each respondent will be asked a series of questions about key facilitators, barriers to availability and overlap in MOUD services (e.g., Narcan/Naloxone, Buprenorphine, and Naltrexone) and COVID services (e.g., testing, vaccine, medication. [e.g., Remdesivir], availability, etc.) provided in pharmacies, as well as access to and distribution (e.g., mail order, drive thru, in person) of different types of Naloxone, Buprenorphine, Naltrexone and other Medications for Opioid use Disorder (MOUD) in pharmacies in NY HCS communities.

The interview will be audio recorded. The recording is for the use of the New York research team in transcribing the interviews and will not be shared with anyone outside of the research team. The recording may include the respondent's name, but it will be removed from the transcribed interview form and a study ID number substituted in its place. The audio files and transcription will be saved on a secure server at Columbia University. Audio files will be destroyed within 6 months following transcription; transcription files will be kept for 3 years following project completion and then destroyed.

The New York research site will analyze the interview transcripts using qualitative data techniques. The team will summarize the results in a report to the New York Research Site's HCS leadership team and may also be included in future publications.

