14	Other respondent-facing material (e.g., email invitation to participate) (specify)	Email invitation, confirmation, and meeting logistics

Focus Group for Persons with OUD		
Main Study Data Collection		
1	Purpose	Message testing to ensure relevance and lower risk of unintended effects of the communication campaign
2	Respondent	People who self-identify as having OUD or using injection opioids
3	How will respondents be selected?	Potential participants will be recruited through print and social media advertisements. We anticipate that some recruitment will also occur through word of mouth in the social and professional networks of coalition members. Participants will be screened to be (1) between ages 18 and 75, (2) a resident of the town or county where the groups will take place, and (3) having a self-reported opioid use disorder or self-reporting use of injection opioids (i.e., heroin, fentanyl) or had an opioid overdose in the past year.
4	Sample size	N=300 across 33 communities; groups will have between 3 and 8 participants each
5	Repeated (Y/N)	Yes
	If yes: frequency (e.g., annually, monthly)	Yes, may be repeated for formative research in subsequent communication campaigns
6	Mode (telephone, web, in person)	In-person or web conferencing, to be determined by each RS
7	Self-administered or interviewer administered	Interviewer administered
8	Informed consent (verbal, written, digital)	Written
9	Incentives (Y/N)	Yes
	If yes: incentive type (e.g., gift card, cash, check)	\$50–\$75 gift card to be determined by the RS
10	Seeking Waiver of Documentation of Informed Consent (Y/N)	No
11	Cross-site or site specific (specify site)	Cross-site
12	Data collection platform (e.g., REDCap, video)	Audio-recording
13	Audio-recording (Y/N)	Yes. Recordings will be saved on secure project servers and deleted after analysis is complete.
14	Other respondent-facing material (e.g., email invitation to participate) (specify)	Email invitation, confirmation, and meeting logistics

Focus Group Testing of Launch Messages		
Main Study Data Collection		
1	Purpose	To understand how people who are aware of the opioid crisis in the community respond to messages about naloxone, OUD, MOUD, and stigma
2	Respondent	Residents in each community

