3	How will respondents be selected?	Pharmacists will be selected because they work for pharmacies in New York's HCS communities. The NYS Pharmacy Association will provide recruitment assistance to the NY research team.  People With Opioid Use Disorder (PWOUD) will be selected/recruited from three types of programs serving PWOUD at sites in NY's HCS counties, with diverse communities: a) Methadone Maintenance treatment programs; b) primary care clinics; c) syringe exchange programs. Recruitment will ensure that the sample includes minority representation across non-Hispanic Blacks and Hispanics.
4	Sample size	20 Pharmacists; 20 People With Opioid Use Disorder
5	Repeated (Y/N)	Yes
	If yes: frequency (e.g., annually, monthly)	Annually
6	Mode (telephone, web, in person)	Telephone/Video Conference
7	Self-administered or interviewer administered	Interviewer administered
8	Informed consent (verbal, written, digital)	Verbal
9	Incentives (Y/N)	Yes
	If yes: incentive type (e.g., gift card, cash, check)	\$50
10	Seeking Waiver of Documentation of Informed Consent (Y/N)	Yes
11	Cross-site or site specific (specify site)	Site Specific (New York)
12	Data collection platform (e.g., REDCap, video)	Video Conference

Pharmacy Study Interview Guide		
13	Audio-recording (Y/N)	Yes
14	Other respondent-facing material (e.g., email invitation to participate) (specify)	See NY Pharmacy Study Survey & Interview Guide Subject Facing Materials .

Pharmacy Study Survey		
Main Study Data Collection		
1	Purpose	To assess racial/ethnic disparities in Medication for Opioid Use Disorder (MOUD) and Naloxone availability at pharmacies in HCS communities., The surveys (one for pharmacy staff or pharmacists and one specifically for licensed pharmacists) will include questions about access to Narcan/Naloxone, Buprenorphine, Naltrexone, Methadone and COVID-19 services in pharmacies located within NY's HCS Communities.
2	Respondent	Pharmacists, pharmacy technicians and/or other pharmacy staff who work for a pharmacy in one of NY's HCS communities.
3	How will respondents be selected?	The NYS Pharmacy Association will provide recruitment assistance to the NY research team that will also conduct an online search for pharmacy contact information. The pharmacist, pharmacy technician and/or other pharmacy staff will work for pharmacies in NY's HCS communities.

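### The New York pharmacy interviews are meant for people with opioid use disorder, but their eligibility sentence requires neither that disorder nor any opioid use

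*Protocol*

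**What the plan says.** Section 12.4.6 of the protocol gives the purpose of the interviews as, in part, to "examine the perspectives of People with Opioid Use Disorder (PWOUD) with respect to barriers to accessing MOUD and Naloxone services in pharmacies". It sets the size "with a goal of interviewing 20 People with Opioid Use Disorder (PWOUD) and 20 pharmacists in HCS communities". The Table 10 entry for the Pharmacy Study Interview Guide repeats that target as "20 Pharmacists; 20 People With Opioid Use Disorder" and names people with OUD as one of its two respondent types.

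The rule for entry then asks for adults who "have used heroin, cocaine, and/or methamphetamine within the past 12 months, and/or received, or currently receive services from an opioid treatment, HIV primary care"; attendance at a syringe exchange is the third service listed. The only check that 12.4.6 describes is staff confirming age and experience of drug use.

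Recruitment and referral run through three kinds of program described as serving people with OUD: a methadone maintenance program, a primary care clinic (not described as an HIV clinic) and a syringe exchange.

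Elsewhere the protocol does screen for OUD. In Table 10, the focus group for persons with OUD and the message-testing interview for persons with OUD share a screen. Besides limits on age and residence, the focus group entry requires "having a self-reported opioid use disorder or self-reporting use of injection opioids (i.e., heroin, fentanyl) or had an opioid overdose in the past year"; the interview entry has the same criterion.

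**The concern.** The named population and the operative rule do not match. The rule lists three drugs, of which one is an opioid, and three services, of which one is opioid treatment, and joins them by and/or. A person can therefore meet it with no opioid use and no OUD.

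It can also miss people it is meant to reach. Fentanyl and prescription opioids are not named, although the protocol's own background (section 2.2) identifies illicit fentanyl and its analogs as the force behind rising overdose deaths.

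What is at stake is the label on the findings. Section 12.4.6 says the results go to the New York site leadership, may be published, and are meant to inform how pharmacies are used to promote MOUD and naloxone in the intervention. Views from someone without OUD would be reported as those of a person with OUD. On access to buprenorphine or naltrexone, that person may have no experience to report.

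**Working it through.** There is no figure in the plan to reproduce: the 20 interviews are a bare target with no derivation. The check is to apply the written rule to every combination of the characteristics it turns on.

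**Inputs (12.4.6).** Limb D: heroin, cocaine or methamphetamine in the past 12 months. Limb S: past or current services from opioid treatment, HIV primary care or a syringe program. Age is taken as met.

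**Two readings of and/or.** Inclusive: eligible if D or S. Strict: eligible if D and S.

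**Profiles.** Seven yes/no items: OUD, heroin, another opioid, cocaine or methamphetamine, opioid treatment, HIV primary care, syringe program.

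**1. No OUD and no opioid use.** Four items are free, so 2^4 = 16 profiles.
- Inclusive: all qualify except the one with nothing, 16 − 1 = 15.
- Strict: stimulant use plus at least one of three services, 1 × (2^3 − 1) = 7.
- Some of these include opioid treatment, which is implausible without an opioid history. Leaving them out gives 2^3 = 8 profiles, of which 8 − 1 = 7 qualify on the inclusive reading and 1 × (2^2 − 1) = 3 on the strict one (stimulant use with HIV primary care, with a syringe program, or with both).

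**2. OUD present.** Six items are free, so 2^6 = 64 profiles.
- Inclusive: a person fails only if D and S are both empty, with or without another opioid: 2 profiles.
- Strict: those who pass number 2 (other opioid yes or no) × 3 (heroin, stimulant or both) × 7 (at least one service) = 42, so 64 − 42 = 22 fail.

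**3. People with OUD who fail, by recruitment source.** The methadone program sets opioid treatment to yes, and the syringe exchange sets syringe program to yes. The primary care clinic sets nothing.

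| Source | Inclusive | Strict |
|---|---|---|
| Methadone program | 0 | 2^3 = 8 |
| Syringe exchange | 0 | 2^3 = 8 |
| Primary care clinic | 2 | 22 |

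On the inclusive reading, exclusion arises only through the primary care clinic. It falls on a person with no past-year use of the three named drugs and none of the listed services, for example someone using only fentanyl or prescription opioids. On the strict reading it reaches a methadone patient who used none of the three drugs in the past year.

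**4. Size.** These are counts of logical cases, not of people, and say nothing about how often each occurs. Each interview is 1/20 = 5% of the target. The documents bound the number of off-target interviews only between 0 and 20.

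**The case against.** The best defence is that the sentence should be read with its subject. It speaks of participants already called people with OUD, Table 10 gives the same respondent type, and referrals come from programs serving them. On that view the listed drugs and services narrow a group whose OUD is already established. The staff check of drug use experience may also bring out opioid use, and the recruitment materials and consent form are not among the documents.

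Much of this is fair, and it makes off-target entry less likely. It does not cure the rule. Primary care clinics and syringe programs also serve people without OUD, and 12.4.6 describes no step that confirms the disorder. If the list is only a further filter, the other half of the problem remains: it would turn away people with OUD whose opioid is not heroin and who meet no other item.

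A reader might also infer that interviews with people without OUD are worthless for the stated aim. The documents do not support that. The aim covers naloxone as well as MOUD, and the ORCCA description in section 6.1.1.4 directs naloxone to high-risk individuals and their social networks and lists syringe service programs among the heightened-risk venues. Such people may have relevant experience of naloxone in pharmacies. The fault lies in the label, and in what can be concluded about MOUD.

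**Conclusion.** The mismatch is real under either reading of and/or: opioid use is not required, and some people with OUD fail the rule. It is minor. This is a small, single-site qualitative activity in Appendix D, with no bearing on the primary outcome, the power or any SAP analysis.

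Two stronger readings should be resisted. A reader might infer that a sizeable share of the 20 interviews is off target. The documents give no share, and any percentage would be an assumption. A reader might also infer that people with OUD outside treatment and syringe programs are generally shut out. On the inclusive reading they are not: past-year use of heroin, cocaine or methamphetamine is enough, as is any past receipt of a listed service, and a patient given buprenorphine in primary care could reasonably count as receiving opioid treatment.

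The conclusion assumes that the sentence in 12.4.6 is the rule staff apply, and that no unseen screening form adds an OUD criterion.

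**What to change.** Reconcile the eligibility sentence with the stated population in 12.4.6 and Table 10. Make self-reported OUD a required criterion, or use an opioid-based one adapted from the two Table 10 screens, naming opioids beyond heroin. This would be an adaptation: those screens also set an upper age and a residence rule, their drug-use route covers injection opioids only, and they admit some people by opioid use or overdose without OUD. Stop treating stimulant use, HIV primary care or syringe-program attendance as sufficient alone, and state plainly whether the remaining conditions are alternatives or all required.

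For interviews already held, attribute findings to people with OUD only where recorded drug-use or treatment information shows that the participant meets the criterion. Otherwise describe the sample as people who use drugs or attend these services. This may be all that can still be done: section 1.2 puts the end of intervention at December 2023. Reclassification may also be impossible for some interviews, because names are removed from transcripts, recordings are destroyed within 6 months of transcription, and 12.4.6 does not say whether screening answers are kept.

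The cost is one sentence and a matching change to any screening script. A few referred people would become ineligible.
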